## 2.2. Hypothesis

No formal statistical hypothesis is planned. The study will evaluate whether Ad26.RSV.preF is safe, well-tolerated and immunogenic in adults and RSV-seropositive toddlers.

## 3. STUDY DESIGN AND RATIONALE

*In this document, unless otherwise specified, any reference to activities to be performed by the subject refers to adult subjects or the parent/legal guardian for pediatric subjects.*

### 3.1. Overview of Study Design

This is a multi-center, randomized, double-blinda, Phase 1/2a study, to be conducted in 12 male and female adults aged  $\geq 18$  to  $\leq 50$  years and 36 male and female toddlers aged  $\geq 12$  to  $\leq 24$  months of age, seropositive for RSV within 42 days prior to dosing.

Subjects will be enrolled into sequential age cohorts:

- 18 to 50 year-old adults, into **Cohort 0**
- 12 to 24 month-old seropositive toddlers, into **Cohort 1**

---

a The administrator of the vaccine may be unblinded but will not participate in any other study evaluation from randomization onwards. The site staff or qualified professional staff who will do the observation and the subjects will be blinded.

In Cohort 0, subjects will be randomized 2:1 to receive either Ad26/Ad26 (at  $1 \times 10^{11}$  vp) or placebo/placebo, and in Cohort 1, subjects will be randomized 2:1 to receive either Ad26/Ad26 (at  $5 \times 10^{10}$  vp) or placebo/placebo (Table 5).

The standard dose ( $5 \times 10^{10}$  vp) is the dose the most commonly used in previous studies and other programs with good safety and immunogenicity profiles. The high dose ( $1 \times 10^{11}$  vp) has been shown in study VAC18192RSV1003 to be well tolerated in elderly subjects and at least as immunogenic, and is therefore appropriate for adults in this study. The standard dose is thought to be the proper dose to start with for preliminary ERD assessment in toddlers as ERD could be linked to a suboptimal immune response. The high dose will be first tested in further studies in seropositive toddlers, before being used in seronegative infants. Dose ranging will be performed in 6-12M seronegative, closer to the target population.

The study will have three phases: a **screening phase**, an **active phase** and a **safety follow-up phase** through 1 year after the first dose. The durations of the respective phases are as follows:

Phase	Cohort 0	Cohort 1
Screening:	up to 4 weeks	up to 6 weeks
Active:	30 weeks 
 
• dosing on Days 1 and 29
 
• safety follow-up through 6 months post-final dose
 
• immunogenicity at:               
 
➤ pre-Dose 1 (Day 1)
 
➤ pre-Dose 2 (Day 29)
 
➤ 28 days post-Dose 2 (Day 57)
 
➤ 6 months post-Dose 2 (Day 211/Week 30)
 
 
 
	30 weeks 
 
• dosing on Days 1 and 29
 
• safety follow-up through 6 months post-final dose
 
• immunogenicity at:               
 
➤ pre-Dose 1 (Day 1)
 
➤ pre-Dose 2 (Day 29)
 
➤ 28 days post-Dose 2 (Day 57)
 
➤ 6 months post-Dose 2 (Day 211/Week 30)
 
 
 

Safety follow-up:	through 1 year after the first dose	through 1 year after the first dose

The end of the active phase will be when the last subject completes the visit at 6 months after the final dose. The end of the study will be the last subject's last visit (by telephone) at the end of the safety follow-up phase.

### First-dose Safety

For Cohort 0, 48-hour and 7-day safety will be monitored by the Principal Investigator(s) (PI[s]) and the Study Responsible Physician(s) (SRP[s])a; for Cohort 1, 48-hour safety will be monitored by the PI(s) and the SRP(s), and 7-day safety will be monitored by the IDMC. In the event of a significant safety finding, the IDMC will be consulted.

*Note:* At least 5 toddlers in the active group are to have received first dose in a clinic setting and

a The safety of Ad26.RSV.preF in elderly subjects at  $5 \times 10^{10}$  vp and  $1 \times 10^{11}$  vp will have been established in study VAC18193RSV1003 prior to initiation of the current study; the purpose of dosing Ad26.RSV.preF in Cohort 0 in the current study is as a safety check for the new drug product formulation buffer, and consequently only PI and SRP review of Cohort 0 safety data is planned prior to dosing seropositive toddlers in Cohort 1.

to have completed Visit 3 with no safety concerns before moving to vaccination of study subjects in a non-clinic setting (safety information of the first 5 active toddlers will be monitored by the PI(s)/SRP(s) through Visit 3, and escalated to the IDMC in the event of a safety signal).

Enrollment will be staggered to allow safety assessments to be made 7 days after the first dose in all 12 adults in Cohort 0 before enrolling and dosing seropositive toddlers in Cohort 1. Additionally, safety assessments will be made 7 days after the first dose in the first 12 seropositive toddlers (8 actives and 4 placebos) in Cohort 1 before enrolling and dosing the remaining seropositive toddlers, as indicated below (see also [Figure 1](#)). In addition, 48-hour safety will be checked after dosing sentinel subjects in both cohorts. The sentinel cohort approach with 2 subjects (1 active and 1 placebo) in each cohort is taken to ensure active and placebo subjects are included in the evaluations, taking into account the blinding. The observation at 48 hours post-dose is primarily to rule out anaphylaxis or cytokine storm.

- Enroll and dose 2 sentinel subjects (adults) in Cohort 0: 1 of these 2 sentinel subjects will receive Ad26.RSV.preF.
- After satisfactory completion of 48-hour safety review after the first dose for these 2 Cohort 0 subjects, the remaining 10 subjects in Cohort 0 will be enrolled and receive the first dose. The PI(s)/SRP(s) will assess post-first dose reactogenicity by review of 7-day safety data for all 12 Cohort 0 subjects.
- After satisfactory completion of this safety review, 2 sentinel subjects (seropositive toddlers) in Cohort 1 will be enrolled and receive the first dose: one of these 2 sentinel subjects will receive Ad26.RSV.preF.
- After satisfactory completion of 48-hour safety review after the first dose for these 2 Cohort 1 subjects, 10 more subjects in Cohort 1 will be enrolled and receive the first dose. The IDMC will assess post-first dose reactogenicity by review of 7-day safety data for the first 12 Cohort 1 subjects (8 actives and 4 placebos).
- After satisfactory completion of this safety review, the remaining subjects in Cohort 1 will be enrolled and receive the first dose.

In all post-first dose 48-hour and 7-day safety reviews, safety data for review will include solicited and unsolicited AEs and SAEs. Additionally, for Cohort 0 safety laboratory data will be included in the 7-day safety review. In the absence of clinically relevant findings, enrollment and dosing for the next cohort of subjects will continue as described above.

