## **5. STUDY VACCINE ALLOCATION AND BLINDING**

### **Study Vaccine Allocation**

Central randomization will be implemented in this study. Within each cohort, subjects will be randomly assigned to one of the two groups based on a computer-generated randomization schedule prepared before the study by or under the supervision of the sponsor. The randomization will be balanced by using randomly permuted blocks. Initially 2 sentinel subjects (one Ad26.RSV.preF and one placebo) will be enrolled to monitor for any unexpected severe adverse reaction to the vaccine. Therefore, the randomization of the first block will be phased to accommodate this. The remainder of the blocks will be filled to have an overall 2:1 randomization ratio. No stratification will be applied. The interactive web response system (IWRS) will assign a unique code, which will dictate the group assignment for the subject. The requestor must use his or her own user identification and personal identification number when contacting the IWRS, and will then give the relevant subject details to uniquely identify the subject.

If randomized subjects are withdrawn from vaccination before the first dose is administered, additional subjects may be recruited to replace these subjects at the discretion of the sponsor. Any replacement subject will be assigned to the same group as the original (discontinued) subject. The replacement subject's randomization number will equal the randomization number of the discontinued subject +1000 (for example subject 0001 would be replaced by subject 1001). These additional subjects should also be randomized through IWRS.

Any randomized subject who is withdrawn from the study for reasons other than due to an AE after the first dose but before the second dose might be replaced at the discretion of the sponsor. Any replacement subject will be assigned to the same group as the original (discontinued) subject. The replacement subject's randomization number will equal the randomization number of the discontinued subject +2000.

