### **Blinding**

The investigator will not be provided with randomization codes until the final analysis is performed. The codes will be maintained within the IWRS, which has the functionality to allow the investigator to break the blind for an individual subject.

Unblinding (ie, at the subject level) will only occur at the time of database lock of the final analysis. While the responsibility to break the study vaccine allocation code in emergency situations resides solely with the investigator, it is recommended that the investigator contact the sponsor or its designee to discuss the particular situation, before breaking the blind. Telephone contact with the sponsor or its designee will be available 24 hours per day, 7 days per week. In such cases, the investigator may in an emergency determine the identity of the study vaccine by contacting the IWRS. In the event the blind is broken, the sponsor must be informed as soon as

possible. The date, time and reason for the unblinding must be documented by the IWRS, in the appropriate section of the electronic case report form (eCRF), and in the source document. The documentation received from the IWRS indicating the code break must be retained with the subject's source documents in a secure manner.

The subjects, study-site personnel, and investigator, and sponsor personnel will be blinded to study vaccine allocation throughout the study, except for the pharmacist or qualified staff member with primary responsibility for study vaccine preparation and dispensing. The pharmacy and preparation of study vaccines will be monitored by an independent study vaccine monitor (see Section 17.8).

*Note:* the unblinded pharmacist, or other qualified individual, may also perform the vaccine administration, but will have no other study function from randomization onwards.

The primary analysis, and any other interim analysis performed before the final analysis, will be performed on data unblinded at the group levela; there will be no unblinding at the subject level. These data will only be available to a selected group of sponsor personnel, excluding sponsor personnel involved in data collection or data management.

In general, randomization codes will be disclosed fully only if the study is completed and the clinical database is closed.

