#### **9.1.4. Screening and Study Visits – Cohort 1 (Seropositive Toddlers)**

*Note:* It is possible for any visit for a pediatric subject to be conducted in the subject's home if the study site has an established standard operating procedure as such. However, at least 5 toddlers in the active group are to have received first dose in a clinic setting and to have completed Visit 3 with no safety concerns before moving to vaccination of study subjects in a non-clinic setting (safety information of the first 5 active toddlers will be monitored by the PI(s)/SRP(s) through Visit 3, and escalated to the IDMC in the event of a safety signal).

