## **11.9. Data Review Committees**

### **11.9.1. Independent Data Monitoring Committee (IDMC)**

An IDMC will be established to review safety data, and as needed on an ad hoc basis to ensure the continuing safety of the subjects enrolled in this study. The IDMC will convene to discuss any situation that meets a study vaccination pausing rule (see Section 11.10).

The IDMC will also monitor severe LRTI. The presence of severe LRTI will be determined by the CEC, a separate committee (see Section 11.9.2). The outcome of the adjudication of the CEC as well as the determination of RSV positivity will be provided to the IDMC.

The IDMC will monitor severe LRTI as detailed in the IDMC charter.

The IDMC will consist of members independent of the sponsor, including at least one medical expert in the relevant therapeutic area and at least one statistician. The IDMC responsibilities, authorities, and procedures will be documented in its charter. An external statistician independent of the sponsor and not involved in the interim, primary, and final analyses of the study will prepare the data and perform all analyses for review by the IDMC.

In any case(s) under review, the IDMC will review blinded data first, but is entitled to and has the right to require submission of unblinded data if deemed necessary.

Individual treatment information and other information essential to maintaining the blinded and controlled study design including the detailed results of the IDMC analyses will not be revealed to anyone outside of the IDMC.

Details on the intervals of the safety evaluations and on how the integrity of the study will be maintained when the blind is broken with an IDMC analysis will be provided in the IDMC charter.

Safety data from the interim and primary analyses will be shared with the IDMC.

If any question arises related to safety, the IDMC will be convened.

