## **1.6. Changes to planned analyses**

Two addition interim analyses for Cohort 1 have been added, for the purpose of informing future vaccine-related decisions in a timely manner. The first interim analysis will be performed when 12 subjects have reached Day 8, and the second one when at least 12 subjects have reached Day 29. Given that the first interim analysis coincides with the planned IDMC analysis, the IDMC members will receive immediately unblinded at the group level safety results instead of blinded, as specified in the CTP. That way the IDMC and the study team will possess the same information regarding safety. Moreover, the conduct of the planned interim analysis, when at least 24 subjects of Cohort 1 have reached Day 29 (28 days post-Dose 1) or discontinued earlier, will be dependent on the outcome of the previous interim analyses and is at the discretion of the sponsor.

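### SAP 1.6 lets an undefined study team hold group-unblinded safety results on the first 12 toddlers without excluding the SRP, who reviews them blinded; the five-active gate has a smaller mismatch

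*Protocol*

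**What the plan says.** SAP 1.6 adds two Cohort 1 interims. The first is triggered when 12 toddlers have reached Day 8 and coincides with the IDMC's 7-day review of those toddlers. The IDMC is to receive group-unblinded instead of blinded safety results, and the section adds: "That way the IDMC and the study team will possess the same information regarding safety". Neither document defines the study team.

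Other sections are narrower. Protocol 5 (Blinding), Protocol 11.8 and SAP 1.5 give interim results only to a selected sponsor group that leaves out staff who collect or manage data. Protocol 5 sets the general rule: "The subjects, study-site personnel, and investigator, and sponsor personnel will be blinded to study vaccine allocation throughout the study", with the vaccine preparer as the exception. Protocol 3.1 (Second-dose Safety) says the sponsor's continuing safety review uses blinded data. Protocol 11.9.1 has the IDMC look at blinded data first. It assigns IDMC analyses to an external statistician with no part in the interim analyses, and says "the detailed results of the IDMC analyses will not be revealed to anyone outside of the IDMC". It also says that interim safety data go to the IDMC.

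The PIs and the SRP monitor the pausing rules (Protocol 11.10) and the 48-hour and 7-day reviews after dose 2. The 7-day review of the first 12 toddlers must be finished before the other toddlers receive dose 2 (Protocol 3.1).

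Separately, vaccination outside the clinic has a condition (Synopsis, Protocol 3.1, Time and Events footnote, Protocol 9.1.4): "at least 5 toddlers in the active group are to have received first dose in a clinic setting" and to have completed Visit 3 without safety concerns. The note continues that "safety information of the first 5 active toddlers will be monitored by the PI(s)/SRP(s) through Visit 3". The unblinded preparer "may also perform the vaccine administration, but will have no other study function from randomization onwards".

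**The concern.** Both issues ask people who are meant to be blinded to act on, or hold, information about allocation.

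The main one is access. The selected-group rule excludes only data-collection and data-management staff. It does not exclude the SRP, and *study team* is looser still. A person who follows events toddler by toddler and also holds an 8-versus-4 table can work out the arm of some individual toddlers. The judgements exposed are the monitoring of the pausing rules and the second-dose review of the same 12 toddlers, both of which Protocol 5 intends to be made blinded.

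The minor one is the gate. It is defined by treatment arm, its named monitors are blinded, the one unblinded site role is barred from helping, and nobody is named to confirm that the condition is met.

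**Working it through.** **1. The plan's own figures.** Protocol 11.2 tabulates the chance of at least one AE as 1 − (1 − p)^N. For N = 12 this gives 46.0%, 71.8% and 96.8% at p = 5%, 10% and 25%, against the stated 46%, 72% and 97%. All 28 cells of the table reproduce. The split of the first 12 toddlers into 8 and 4 is stated in Protocol 3.1 and follows from 2:1.

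**2. What an 8-versus-4 table shows to someone who also holds subject-level events.** The arms of all affected toddlers are revealed when all of them fall in one arm. With m affected toddlers and no vaccine effect, the chance of this is [C(8,m) + C(4,m)] / C(12,m):

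- m = 1: 12/12 = 100%
- m = 2: (28 + 6)/66 = 52%
- m = 3: (56 + 4)/220 = 27%

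For one AE term with true rate p in both arms and q = 1 − p, the chance that it occurs and falls in one arm only is R = q⁴(1 − q⁸) + q⁸(1 − q⁴). Dividing by 1 − q¹² conditions on the term occurring at all.

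| p | R | 1 − q¹² | R given that the term occurs |
|---|---|---|---|
| 5% | 0.397 | 0.460 | 86% |
| 10% | 0.522 | 0.718 | 73% |
| 25% | 0.353 | 0.968 | 36% |

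These figures assume that toddlers are independent, that the table is by AE term, and that its reader also sees individual events. The dummy identifiers in the Protocol 5 footnote do not prevent this, because the match is made on the event and not on the number.

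**3. Timing.** The interim is triggered when the twelfth toddler is at Day 8. That toddler's 7-day visit after dose 2 is nominally Day 36, which is 36 − 8 = 28 days later. Dose 2 is due at Day 29 ± 3, so toddlers first dosed about 18 to 24 days or more before the twelfth may already have had it. The second-dose review of the 12 as a group is still open.

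**4. The gate.** With 4 placebos among the first 12, n dosed toddlers include at least n − 4 actives. That is 5 at n = 9. The sentinel pair holds one placebo, so five actives cannot be reached before the sixth toddler. A blinded reviewer is therefore unsure only at toddlers 6 to 8. Protocol 5 allows certain dosed toddlers to be replaced, and "Any replacement subject will be assigned to the same group as the original (discontinued) subject". One replaced placebo makes the minimum n − 5, so certainty comes at the tenth toddler.

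Unblinded confirmation before that point would leak allocation. Confirmation at the sixth toddler means 5 actives and 1 placebo. The placebo is in the sentinel pair, so toddlers 3 to 6 would all be known to be active.

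**The case against.** The strongest objection is that the interim is allowed. Protocol 11.8 permits extra group-level interims, and Protocol 11.9.1 sends interim safety data to the IDMC. A reader might infer that SAP 1.6 hands the IDMC's results to the study team in breach of 11.9.1. The text does not support that: it brings the IDMC up to what the sponsor's own interim already shows. SAP 3 promises a separate SAP for the IDMC analysis, and 11.9.1 leaves protection of integrity to a charter. All this stands. What remains is that, when one analysis serves both purposes, its content is known outside the IDMC. SAP 1.6 declares the departure from blinded-first review but does not address the non-disclosure and separate-statistician clauses.

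A reader might also infer from SAP 1.5, which leaves sponsor personnel out of its blinded list, that blinding has been relaxed. It has not: SAP 1.5 keeps the selected-group limit and refers to Protocol Section 5.

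It is fair to say that no text places the SRP in the study team, and that the tables actually produced are set in a separate specification. The percentages are therefore conditional and do not show that harm occurred. It is also fair that small tables are planned elsewhere: the Cohort 0 primary analysis is 8 versus 4 too. That one, however, waits until Day 57, after the 7-day review of dose 2.

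The consequences are limited. Investigators stay blinded in both documents, so causality grading, on which most pausing rules turn, is not touched. The allocation of the other 24 toddlers is not revealed, and no hypothesis is tested.

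On the gate, a reader might infer that it cannot be applied under the blind, or might calculate how often it would be declared too early. The first is wrong by step 4. For the second, nothing in the documents says that it would be declared before it is certain.

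**Conclusion.** The main point stands as a gap in access rules that is cheap to close, not as a breach. SAP 1.6 uses a looser term than SAP 1.5 and Protocol 5 and 11.8 for who holds group-unblinded results on 12 toddlers. None of these texts keeps those results from the SRP, whose reviews of the same toddlers are meant to be blinded. If the SRP or a similar reviewer sees the table, a single-toddler event gives away that toddler's arm. An AE term that occurs does so for all affected toddlers in 86%, 73% or 36% of cases at true rates of 5%, 10% or 25%. These figures rest on that unconfirmed access, on tables by term, and on equal rates in both arms.

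The gate point is minor. The condition and the blinding rule do not fit together as written, but absent replacement the condition is certain at nine of the first 12 toddlers. The remaining toddlers also wait for the IDMC's review of all 12.

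**What to change.** - **SAP 1.6:** replace the study team with the selected sponsor group of SAP 1.5 and Protocol 5. State that it excludes the SRP and anyone else who makes blinded subject-level safety decisions. Cross-refer to Protocol 11.9.1, and say how the non-disclosure and separate-statistician clauses apply when one analysis is both the sponsor interim and the IDMC review.
- **Gate note (all four places):** reconcile it with Protocol 5 without changing the clinical threshold. The text can note that, absent replacement, any nine of the first 12 toddlers contain at least five actives, so the existing condition can be verified under the blind. Unblinded confirmation before then should be avoided, because it would reveal allocation.
- **Study report:** Amendment 4 reports 35 toddlers enrolled, so new wording cannot govern the 12-toddler interim after the fact. State who received those tables and how the gate was confirmed. The SAP wording still applies to any further interim.

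The cost is a few sentences and a shorter sponsor distribution list. No analysis, sample size or clinical rule changes.
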